### 14.1.3.2.8 Handling of patients with non-measurable disease only at baseline

It is possible that patients with only non-measurable disease present at baseline are entered into the study, either because of a protocol violation or by design (e.g. in Phase III studies with PFS as the primary endpoint). In such cases the handling of the response data requires special consideration with respect to inclusion in any analysis of endpoints based on the overall response evaluations.

It is recommended that any patients with only non-measurable disease at baseline should be included in the main (ITT) analysis of each of these endpoints.

Although the text of the definitions described in the previous sections primarily relates to patients with measurable disease at baseline, patients without measurable disease should also be incorporated in an appropriate manner. The overall response for patients with measurable disease is derived slightly differently according to [Table 14-4](#).

**Table 14-4 Overall lesion response at each assessment: patients with non-target disease only**

Non-target lesions	New Lesions	Overall lesion response
CR	No	CR
Non-CR/Non-PD 	No	Non-CR/non-PD
UNK	No	UNK
PD	Yes or No	PD
Any	Yes	PD

 As defined in [Section 14.1.2.4](#).

In general, the **non-CR/non-PD response** for these patients is considered equivalent to an SD response in endpoint determination. In summary tables for best overall response patients with only non-measurable disease may be highlighted in an appropriate fashion e.g. in particular by displaying the specific numbers with the non-CR/non-PD category.

In considering how to incorporate data from these patients into the analysis the importance to each endpoint of being able to identify a PR and/or to determine the occurrence and timing of progression needs to be taken into account.

**For ORR** it is recommended that the main (ITT) analysis includes data from patients with only non-measurable disease at baseline, handling patients with a best response of CR as “responders” with respect to ORR and all other patients as “non-responders”.

**For PFS**, it is again recommended that the main ITT analyses on these endpoints include all patients with only non-measurable disease at baseline, with possible sensitivity analyses which exclude these particular patients. Endpoints such as PFS which are reliant on the determination and/or timing of progression can incorporate data from patients with only non-measurable disease.

#### 14.1.3.2.9 Sensitivity analyses

This section outlines the possible event and censoring dates for progression, as well as addresses the issues of missing tumor assessments during the study. For instance, if one or more assessment visits are missed prior to the progression event, to what date should the progression event be assigned? And should progression event be ignored if it occurred after a long period of a patient being lost to follow-up? It is important that the protocol and RAP specify the primary analysis in detail with respect to the definition of event and censoring dates and also include a description of one or more sensitivity analyses to be performed.

Based on definitions outlined in [Section 14.1.3.2.7](#), and using the draft FDA guideline on endpoints ([Clinical Trial Endpoints for the Approval of Cancer Drugs and Biologics-April 2005](#)) as a reference, the following analyses can be considered:

**Table 14-5 Options for event dates used in PFS, TTP, duration of response**

Situation		Options for end-date (progression or censoring)  (1) = default unless specified differently in the protocol or RAP	Outcome
A	No baseline assessment	(1) Date of randomization/start of treatment 	Censored
B	Progression at or before next scheduled assessment	(1) Date of progression (2) Date of next scheduled assessment 	Progressed Progressed
C1	Progression or death after exactly one missing assessment	(1) Date of progression (or death) (2) Date of next scheduled assessment 	Progressed Progressed
C2	Progression or death after two or more missing assessments	(1) Date of last adequate assessment  (2) Date of next scheduled assessment  (3) Date of progression (or death)	Censored Progressed Progressed
D	No progression	(1) Date of last adequate assessment	Censored
E	Treatment discontinuation due to 'Disease progression' without documented progression, i.e. clinical progression based on investigator claim	(1) N/A (2) Date of discontinuation (visit date at which clinical progression was determined)	Ignored Progressed
F	New anticancer therapy given	(1) Date of last adequate assessment (2) Date of secondary anti-cancer therapy (3) Date of secondary anti-cancer therapy (4) N/A	Censored Censored Event Ignored
G	Deaths due to reason other than deterioration of 'Study indication'	(1) Date of last adequate assessment	Censored (only TTP and duration of response)
 =Definitions can be found in Section 14.1.3.2.7 .			
 =After the last adequate tumor assessment. "Date of next scheduled assessment" is defined in Section 14.1.3.2.7 .			
 =The rare exception to this is if the patient dies no later than the time of the second scheduled assessment as defined in the protocol in which case this is a PFS event at the date of death.			

The primary analysis and the sensitivity analyses must be specified in the protocol. Clearly define if and why options (1) are not used for situations C, E and (if applicable) F.

Situations C (C1 and C2): Progression or death after one or more missing assessments: The primary analysis is usually using options (1) for situations C1 and C2, i.e.

- (C1) taking the actual progression or death date, in the case of only one missing assessment.
- (C2) censoring at the date of the last adequate assessment, in the case of two or more consecutive missing assessments.

In the case of two or missing assessments (situation C2), option (3) may be considered jointly with option (1) in situation C1 as sensitivity analysis. A variant of this sensitivity analysis consists of backdating the date of event to the next scheduled assessment as proposed with option (2) in situations C1 and C2.

**Situation E: Treatment discontinuation due to 'Disease progression' without documented progression:** By default, option (1) is used for situation E as patients without documented PD should be followed for progression after discontinuation of treatment. However, option (2) may be used as sensitivity analysis. If progression is claimed based on clinical deterioration instead

of tumor assessment by e.g. CT-scan, option (2) may be used for indications with high early progression rate or difficulties to assess the tumor due to clinical deterioration.

**Situation F: New cancer therapy given:** the handling of this situation must be specified in detail in the protocol. However, option (1), i.e. censoring at last adequate assessment may be used as a default in this case.

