- Addition of the new tumor biopsy sample collection at time of disease progression

Section 7.1.2.2 Patient demographics and other baseline characteristics:

- Addition of the collection of information regarding the status of EGFR and ALK mutations for NSCLC and BRAF V600 mutation status for melanoma in the phase II part of the study.

Section 7.1.3 Treatment period:

- Deletion of redundant text

Section 7.1.4 Discontinuation of study treatment:

- Deletion of text that does not apply in this protocol

Section 7.1.6 Follow-up period:

- Addition of the 60 day and 90 day safety follow-up and associated assessments
- Clarification that also in case of clinical progression, the patient would not be followed for disease progression.
- Addition of the reference to the end of post treatment phase disposition CRF.

Table 7-2 Disease assessment collection plan

- Addition of wording relating to the disease progression follow-up to align with the text in Section 7.2.1.

- Correction of the Table 7-2 regarding the requirement for brain CT/MRI to align with standard clinical practice.

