### 7.1.6 Follow up period

All patients must have safety evaluations for 150 days after the last dose of study treatment. The evaluations can be done either by telephone call or visit for the 30-, 90-, and 150-day safety follow-up visits. Concomitant medications will be collected until the 30-day safety follow-up has been completed or the start of new antineoplastic therapy, whichever occurs first. If the 150-day safety evaluation is conducted by phone, samples do not need to be collected. Data collected should be added to the Adverse Events CRF, the antineoplastic therapies since discontinuation of study treatment CRF, the Concomitant Medications CRF, Biomarker blood sample CRF, and PK [REDACTED] CRFs. For PK [REDACTED] samples and Biomarker samples collection schedule is outlined in [Section 7.2.3](#) and [Section 7.2.4](#) respectively. For female patients of child bearing potential, pregnancy tests will be performed as outlined in [Section 7.2.2.5.7](#).

Patients who discontinue study treatment for any reason other than death, disease progression per irRC, clinical progression, lost to follow-up, consent withdrawal, start of new cancer therapy or study termination, also should return for tumor evaluation assessments and should not be considered withdrawn from the study until 80% of the patients in each disease group of the

phase II part have had progression of disease or discontinued the study for any reason. If patients refuse to return for these visits or are unable to do so, every effort should be made to contact them or a knowledgeable informant by telephone to determine if the patient had disease progression. Once the Follow up for Disease progression period ended, the End of Post treatment Phase disposition CRF should be completed.

Upon completion of the 150-day follow up or/and disease progression follow up, patients will be followed for survival every 3 months (can be done by telephone call) until death or until the end of the study is reached, unless they withdraw consent or are lost to follow-up.

Antineoplastic therapies since discontinuation of study drug will be collected during this follow-up period.

For patients who transfer to another clinical study or an alternative treatment option to continue provision of study treatment, as described in [Section 4.3](#), the follow-up for 150-day safety, disease progression and survival will not be performed.

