##### **14.1.4.5.6 Censoring reason**

In order to summarize the various reasons for censoring, the following categories will be calculated for each time to event variable based on the treatment completion page, the study evaluation completion page and the survival page.

For survival the following censoring reasons are possible:

- Alive
- Lost to follow-up

For PFS and TTP (and therefore duration of responses) the following censoring reasons are possible:

- Ongoing without event
- Lost to follow-up
- Withdrew consent
- Adequate assessment no longer available\*
- Event documented after two or more missing tumor assessments (option
- Death due to, see [Table 14-5](#)) to reason other than underlying cancer (*only used for TTP and duration of response*)
- Initiation of new anti-cancer therapy

\*Adequate assessment is defined in [Section 14.1.3.2.7](#). This reason is applicable when adequate evaluations are missing for a specified period prior to data cut-off (or prior to any other censoring reason) corresponding to the unavailability of two or more planned tumor assessments prior to the cut-off date. The following clarifications concerning this reason should also be noted:

- This may be when there has been a definite decision to stop evaluation (e.g. reason="Sponsor decision" on study evaluation completion page), when patients are not followed for progression after treatment completion or when only UNK assessments are available just prior to data cut-off).
- The reason "Adequate assessment no longer available" also prevails in situations when another censoring reason (e.g. withdrawal of consent, loss to follow-up or alternative anti-cancer therapy) has occurred more than the specified period following the last adequate assessment.
- This reason will also be used to censor in case of no baseline assessment.

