4.3 Event dates used in PFS and DOR

Based on definitions outlined in [CPDR001X2101 Amendment 8 Section 14.1.3.2.9], the following analyses can be considered:

Table 4-2 Options for event dates used in PFS and DOR

Situation		Options for end-date (progression or censoring) ¹	Outcome
		(1) = default unless specified differently in the protocol or RAP	
A	No baseline assessment	(1) Date of randomization/start of treatment ³	Censored
В	Progression at or before next scheduled assessment	(1) Date of progression (2) Date of next scheduled assessment ²	Progressed Progressed
C1	Progression or death after exactly one missing assessment	(1) Date of progression (or death)(2) Date of next scheduled assessment²	Progressed
C2	Progression or death after two or more missing assessments	 (1) Date of last adequate assessment² (2) Date of next scheduled assessment² (3) Date of progression (or death) 	Censored Progressed Progressed
D	No progression	(1) Date of last adequate assessment	Censored
E	Treatment discontinuation due to 'Disease progression' without documented progression, i.e. clinical progression based on investigator claim	(1) N/A (2) Date of discontinuation (visit date at which clinical progression was determined)	Ignored Progressed
F	New anticancer therapy given	, ,	Censored Censored Event Ignored
G	Deaths due to reason other than deterioration of 'Study indication'	(1) Date of last adequate assessment	Censored (only TTP and duration of response)

	,	
•	Options for end-date (progression or censoring) ¹	Outcome
	(1) = default unless specified differently	
	in the protocol or RAP	

- 1. =Definitions can be found in [CPDR001X2101 Amendment 8 Section 14.1.3.2.7]
- 2. =After the last adequate tumor assessment. "Date of next scheduled assessment" is defined [CPDR001X2101 Amendment 8 Section 14.1.3.2.7].
- 3. =The rare exception to this is if the patient dies no later than the time of the second scheduled assessment as defined in the protocol in which case this is a PFS event at the date of death.

5 References

Chen M, Ibrahim J (2006) The Relationship Between the Power Prior and Hierarchical Models, Bayesian Analysis, 1, Number 3.

Deeks ED (2014) Nivolumab: A review of its use in patients with malignant melanoma. Drugs; 74:1233-39.

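### PFS ignores clinical progression because such patients are to be followed, yet Protocol 7.1.6 ends their tumour evaluation; no sensitivity analysis for them is committed, so PFS rates lean slightly upward

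*Protocol*

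**What the plan says.** **The default.** Row E of Protocol Table 14-5 covers clinical progression without documented progression. SAP Table 4-2 repeats it: "Treatment discontinuation due to 'Disease progression' without documented progression, i.e. clinical progression based on investigator claim". Option (1), the default in both tables, ignores it. Option (2) counts an event at the visit where clinical progression was determined. The text on Situation E in Protocol 14.1.3.2.9 explains the default: "By default, option (1) is used for situation E as patients without documented PD should be followed for progression after discontinuation of treatment".

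**The follow-up rule.** Protocol 7.1.6 says who returns for tumour evaluation after treatment: "Patients who discontinue study treatment for any reason other than death, disease progression per irRC, clinical progression, lost to follow-up", followed by further exceptions. Clinical progression is one of the exceptions. The Amendment 03 change log agrees with this current text and shows the exclusion was deliberate: "Clarification that also in case of clinical progression, the patient would not be followed for disease progression". Section 4.1 likewise excludes patients who stop for disease progression from progression follow-up.

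**Sensitivity analyses.** Protocol 14.1.3.2.9 wants the protocol and RAP to "also include a description of one or more sensitivity analyses to be performed". For row E it says only: "However, option (2) may be used as sensitivity analysis". SAP 4.3 introduces its copy of the table with "the following analyses can be considered". The SAP names two other time-to-event sensitivity analyses, both optional: censoring unconfirmed irPD (3.4 and 4.2.4.1) and censoring at palliative radiotherapy (3.4). Neither touches row E.

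**The concern.** The default is defensible where imaging continues after clinical progression, because a later scan can then supply the event. Here imaging stops. A patient who stops treatment for symptomatic deterioration has no route to a documented progression unless the end-of-treatment scan shows one. Kaplan-Meier then treats that patient as having the same outlook as those still at risk at the last scan, although the patient left because of deterioration. The error has a known direction: PFS rates come out too high.

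The PFS rates at 3, 6, 9 and 12 months reported for each Phase II group (SAP 3.4.2) are exposed to this. No planned run would show a reader how far they depend on the choice.

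**Working it through.** **What happens to a row E patient under the plan**

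1. The clinical progression itself is ignored (row E, option 1).
2. Survival follow-up continues (7.1.6), so a later death is captured. It is a PFS event if at most one assessment was missed (row C1).
3. A death after two or more missed assessments is censored at the last adequate assessment (row C2, option 1). With no death the patient is censored there too (row D), or at treatment start if there was no post-baseline scan (14.1.3.2.7).
4. Protocol 14.1.4.5.6 allows for this. Its category for adequate assessment no longer being available applies "when patients are not followed for progression after treatment completion".

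**Size.** The documents give no PFS design figure and no row E frequency, so there is nothing to reproduce and the inputs below are partly assumed.

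- From the protocol: scans every 8 weeks to week 40, then every 12.
- Assumed: exponential progression with median 8, 12, 16 or 20 weeks; a share of 2%, 5% or 10% with clinical progression only; median survival after it of 4, 13 or 26 weeks; no end-of-treatment scan; no new therapy. Each scenario has 400,000 simulated patients.
- Plan rule: event at death if no later than the second scheduled scan after the last one, otherwise censored at the last scan.
- Like-for-like comparator: row E event dated at the next scheduled scan, as documented progression would be.

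The comparator has a closed form. PFS at 26 weeks equals the probability of no progression by the week-24 scan, 0.5^(24/median). For a 20-week median this is 0.5^1.2 = 43.5% (simulated 43.4%); for an 8-week median it is 0.5^3 = 12.5% (simulated 12.4%).

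Plan minus comparator, in percentage points, over the four progression medians:

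| Row E share | Survival 4 wk: at 13 wk | Survival 4 wk: at 26 wk | Survival 13-26 wk: at 13 wk | Survival 13-26 wk: at 26 wk |
|---|---|---|---|---|
| 2% | about 0 | +0.1 to +0.2 | +0.2 to +0.4 | +0.2 to +0.5 |
| 5% | 0 to +0.1 | +0.3 to +0.4 | +0.5 to +1.0 | +0.6 to +1.3 |
| 10% | 0 to +0.1 | +0.5 to +0.7 | +1.0 to +2.0 | +1.3 to +2.6 |

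With 4-week survival about 90% of these patients become events by death, which is why that lean is so small.

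**Dating.** Option (2) dates the event before the next scan, so part of its gap from the plan is only earlier dating. Two examples at a 10% share and a 20-week median:

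- 13-week PFS, 13-week survival: plan 76.8%, next-scan dating 75.7%, option (2) 74.5%. The gap to option (2) is 76.8 - 74.5 = 2.3 points, of which 75.7 - 74.5 = 1.2 is dating.
- 26-week PFS, 26-week survival: 46.0%, 43.4% and 43.2%. The gap is 2.8 points, of which 0.2 is dating.

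**Scale.** At 40% PFS the 90% half-width, ignoring censoring, is 1.645 x sqrt(0.4 x 0.6 / 60) = 10.4 points for n = 60 and 1.645 x sqrt(0.24 / 42) = 12.4 points for n = 42. A 10% share is 6 of 60 patients or about 4 of 42.

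**The case against.** The analysis rule is not ambiguous. Both tables mark option (1) as the default, and the appendix asks authors to justify departing from option (1), not keeping it. The sentence giving the reason is standard appendix text, while 7.1.6 is what sites follow. This stands, and it limits the defect to a reason that does not apply plus an alternative left optional.

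Several features also shrink the effect. Protocol 8.2.1 expects clinical-only determinations to be rare. Patients should not stop on RECIST progression alone (4.1), so many who deteriorate will already have a RECIST event. An end-of-treatment scan is due if none was done in the prior 30 days (7.2.1). A single irPD before stopping counts as an irRC event (SAP 4.2.2.2). All of this stands.

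Three stronger readings are tempting, and the documents do not support them.

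- **The plan breaks its own rule on row E.** 14.1.3.2.9 asks for one or more sensitivity analyses and does not say that row E must be among them.
- **These patients are hidden.** End-of-treatment reasons, per-patient PFS listings and event and censoring counts are planned (SAP 3.1.1, 3.4.2), and such discontinuations are to be reviewed (Protocol 14.1.4.4). The output shells are in a separate document, so what they isolate cannot be judged here.
- **The bias is large.** A separate simulation reached about 13 points at 3 months against option (2), but only with a 30% share and half of these patients starting new therapy. Nothing in the documents points to such a share.

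**Conclusion.** The point holds as a minor one. The only stated ground for ignoring clinical progression is contradicted by the trial's own follow-up rule, and no analysis that would show the consequence is committed.

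The direction is upward. The size rests on assumed shares and survival times: about 0 to +2.0 points at 13 weeks and +0.1 to +2.6 at 26 weeks, less where an end-of-treatment scan documents progression. These are not bounds. A larger share would raise them, as would new therapy that turns later deaths into censored times. They are small beside half-widths of 10-12 points.

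The anaplastic thyroid group deserves a look. Situation E itself suggests option (2) where early progression is frequent, and the Amendment 06 rationale reports that most early patients in that group progressed or died before the first scheduled scan. Short survival would, however, turn many of them into events by death and reduce the lean.

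No decision rule uses PFS, and the primary ORR result does not change.

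**What to change.** 1. Reconcile the Situation E rationale in Protocol 14.1.3.2.9 with Section 7.1.6, so that the reason given for the default fits the follow-up actually planned.
2. Keep documented progression as the main PFS definition.
3. In SAP 4.3, commit for each Phase II group to one PFS sensitivity analysis that sets row E to option (2) and changes nothing else. Read it mainly at 6 months, because earlier dating inflates the 3-month difference.
4. Report per group the number of row E patients and how each was handled: event by death, censored at a scan, or censored at treatment start. Identify them as end of treatment for disease progression (a reason listed in SAP 2.1.2) without documented progression. Say how this maps to the recorded reasons, since the list in Protocol 7.1.4 has irRC progression but no clinical-progression entry.

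The cost is some wording, one extra PFS run and one count line per group, using an option already in the sponsor's table. No new data are needed. The drawback is that clinical progression is less objective than imaging, which is why this should remain a sensitivity analysis.
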